8.4. Injection Site Reactions

A summary table of ISRs will include numbers of events, and numbers and percentages of subjects, experiencing a) any ISR; b) ISRs documented as adverse events on CRF data (per protocol criteria); and c) hypopigmentation events. Exact Cochran-Armitage tests of trend will be used to explore relationships between MPA dose and the probability of experiencing ISRs.

ISRs will be further tabulated according to specific categories, including but not necessarily limited to erythema, swelling, pruritus, bleeding, bruising, hypopigmentation, atrophy, and injection site pain. The maximum recorded size of ISRs (if applicable) will be summarized using descriptive statistics for continuous variables. An 11-point numeric rating scale will be used to describe reports of injection site pain. Listings of ISRs will include time to onset, duration,

Statistical Analysis Plan Version 5.0

Pharmacokinetics Study–Healthy Subjects

Study TV46046-WH-10159

outcome, and whether the ISR was self-reported by the subject or noted by clinic staff when performing an assessment of the injection site.

8.5. Delayed Return to Ovulation

The number and percentage of subjects with no evidence of ovulation (i.e. no observed $P \geq 4.7$ ng/mL) in the 12th month of follow-up, and an exact 95% CI for the probability of delayed return to ovulation based on a binomial distribution assumption, will be reported by treatment group. These calculations will exclude subjects with 1 or more missing progesterone measurements at weeks 48, 49, 50, 51 or 52 unless ovulation was detected at one of their non-missing visits.

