3.4.3. Procedures for Follow-Up

Study follow-up will last for at least 52 weeks from treatment initiation. There will be four scheduled follow-up visits at Week 1 (Day 7), Week 13, Week 26, and Week 52, during which subjects will be evaluated for vital signs, body weight, liver enzymes, ISRs, adverse events and

use of concomitant medications. Vaginal bleeding pattern, acceptability and mood will be evaluated throughout the study at pre-defined time points (See [Table 1](#)). Urine pregnancy tests will be administered periodically starting at Week 26 through the end of the study.

In addition to the scheduled follow-up visits, subjects will return for laboratory visits to provide blood samples for MPA, P, and E2 at pre-defined time points (see [Table 1](#)).

If the subject has new or ongoing ISRs at Week 52, she will be followed every 3 months (at Weeks 65 and 78) until ISR resolution or Month 18 (Week 78), whichever is earlier. If the subject does not have any ISRs at Week 52 it will be her final visit. However, all subjects will be instructed to return to the clinic if any ISRs develop after their final visit. In that case, their status will change from completed the study to active and they will be followed per the schedule above until ISR resolution or Week 78, whichever is earlier.

Follow up visits should be scheduled using the target window periods below. However, if a subject cannot attend a visit within the target window below, the visit procedures should be conducted as soon as possible regardless of timing.

Table 2: Target Time Windows for Follow-up Visits

Target visit date	Target time window
Days 1, 2	± 1 hour
Days 3, 5, 7	± 3 hours
Days 10, 12, 14, 18	± 24 hours
Any scheduled clinic or laboratory visit past Day 21	± 48 hours

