Statistical Analysis Plan Version 5.0

Pharmacokinetics Study–Healthy Subjects

Study TV46046-WH-10159

INTRODUCTION

This Statistical Analysis Plan (SAP) describes the planned analysis for *A Randomized, Dose-range Finding Study to Evaluate Pharmacokinetics of Medroxyprogesterone Acetate Following a Single Subcutaneous Administration of TV-46046 in Healthy Women of Reproductive Age*. The study is sponsored by Teva Branded Pharmaceutical Products R&D, Inc. and is implemented by FHI 360.

The reader of this SAP is encouraged to read the protocol for details on the conduct of this study, the operational aspects of clinical assessments, and the timing for completing the participation of a subject in this study. Version 1.0 of the SAP expands upon the analysis of primary and secondary endpoints outlined in Protocol Amendment 01 (the current version at the time of first subject enrolled), including definitions of estimands and methods for handling missing data and intercurrent events. When differences exist in descriptions or explanations provided in the study protocol and this Statistical Analysis Plan, the SAP prevails; any such differences will be explained in the Clinical Study Report (CSR).

Future changes to the SAP (e.g., to address amendments to the protocol) and their temporal relationship to unblinding will be documented in Section 12 and detailed in the CSR. Mock tables, figures and listings will be approved by the Coordinating Investigator prior to un-blinding of study statisticians and maintained in a separate document.

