4.3. Handling of Withdrawals and Missing Data

4.3.1. Discontinuation and Missing Data

Subjects who are discontinued from the study after being randomized will not be replaced. All available data up to the time of discontinuation will be included in relevant analyses. Except as noted in Section 4.3.2, missing data will not be estimated or imputed.

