4.3.2. Imputed Data

Missing MPA concentrations at key time points (e.g., end-times of partial AUCs) and MPA concentrations that fall below the lower limit of quantification (LLOQ) will be imputed using methods specified in Section 10. Other laboratory measurements that fall below an applicable LLOQ will be imputed as half the LLOQ when summarizing continuous variables. If required to interpret safety, incomplete adverse event onset, resolution, or concomitant medication use dates may be imputed as follows:

- If the month of adverse event onset or initiation of medication use is known but the day is missing, then the onset/initiation date may be imputed as the first day of the month.
- If the month of adverse event resolution or medication use stop-date is known but the day is missing, then the resolution/stop data may be imputed as the last day of the month.

Other imputation rules may be required on a case-by-case basis, as determined by the Coordinating Investigator or delegated staff member. Imputation decisions will be documented in the CSR as occurring after unblinding, as applicable.

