10.7. Planned Sensitivity Analyses

The NCA analysis will be repeated based on the Safety Set (not excluding any subjects or data points, regardless of IEs or violations of entry criteria). In addition, if more than 10% of subjects have missing data on visit Day 91, 182, or 210 then the primary comparison of those outcomes between test and reference groups will be repeated based on imputed C_{91} , C_{182} , or C_{210} values, using the same imputation rules as for the end-times of partial AUCs.

10.8. [REDACTED]

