12. CHANGES TO PLANNED ANALYSES

12.1. Changed from V1.0 of the SAP

The following cumulative changes were made from Version 1.0 of the SAP, prior to unblinding:

Version 2.0 (May 18, 2021)

- Section 1.2.2: Safety and local tolerability measures/parameters updated to be consistent with changes made in Protocol Amendment 02.
- Section 2.1: revised to reflect updates to assessment timepoints in Table 1 of the protocol. Specifically, addition of collection of P specimens and mood evaluation on Day 0; specimens for E2 collected on Day 0 and weeks 48, 49, 50, 51 and 52; and clarifying which visits E2 specimens will be collected if MPA or P samples are taken (starting on Day 28).
- Section 10.7: [REDACTED].

Version 3.0 (April 12, 2022)

Version 3.0 of the SAP was created to document that the above changes took place.

Version 4.0 (June 29, 2022)

Version 4.0 of the SAP clarified computation methods for apparent half-life and time above 0.2 ng/mL. The imputation of partial AE and concomitant medication start and stop dates using previous visit dates was removed as reporting date for these events was not collected. Changes to planned analyses were documented and approved prior to unblinding.

Version 5.0 (February 15, 2023)

Version 5.0 of the SAP expanded the analysis visit windows in Table 2 after blinded review of samples excluded for being out of window. These changes were not implemented for the interim analysis but were documented and approved prior to unblinding. In section 8.5, the definition of ovulation in month 12 was added as well as a definition of which subjects would be included in the denominator for the percentage calculations.

Certificate Of Completion

Envelope Id: 16B2332D2490446EBC283C9E93E0087A

Status: Completed

Subject: TV46046-10159 SAP V5.0.doc

CF02:

Project Code/Charge Code: FP0205.C01.004.004.001

Source Envelope:

Document Pages: 26

Signatures: 2

Envelope Originator:

Certificate Pages: 5

Initials: 0

[REDACTED]

AutoNav: Enabled

[REDACTED]

EnvelopeD Stamping: Enabled

[REDACTED]

Time Zone: (UTC-05:00) Eastern Time (US & Canada)

[REDACTED]

IP Address: [REDACTED]

Record Tracking

Status: Original

Holder: [REDACTED]

Location: DocuSign

2/15/2023 10:56:37 AM

Signer Events**Signature****Timestamp**

Family Health International Inc - Part 11

Security Level: Email, Account Authentication
(Required)

[REDACTED]

Sent: 2/15/2023 10:58:30 AM

[REDACTED]

Viewed: 2/17/2023 9:32:59 AM

[REDACTED]

Signed: 2/17/2023 9:34:03 AM

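### SAP 8.5 removes a partly sampled woman only when no ovulation was seen, so the delayed-return percentage is selected on its own outcome; report exclusion counts and two-way bounds beside it (minor)

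*SAP*

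**What the plan says.** Protocol Table 1 schedules progesterone at Day 0 and at Weeks 48, 49, 50, 51 and 52. Protocol 5.1.8 treats one value of 4.7 ng/mL or more as confirming ovulation, and Protocol 9.6 lists delayed return to ovulation among the safety evaluations.

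SAP 8.5 reports "The number and percentage of subjects with no evidence of ovulation" in month 12, by treatment group, with an exact binomial 95% CI. It then sets the denominator: "These calculations will exclude subjects with 1 or more missing progesterone measurements at weeks 48, 49, 50, 51 or 52 unless ovulation was detected" at a visit the woman did attend. SAP 12.1 records that Version 5.0 added the "definition of which subjects would be included in the denominator for the percentage calculations".

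Other text that bears on missing samples:

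- Protocol 3.4.3: if a visit cannot be made within its window, "the visit procedures should be conducted as soon as possible regardless of timing".
- SAP 4.3.1: "Except as noted in Section 4.3.2, missing data will not be estimated or imputed".
- SAP 4.3.2: "Other imputation rules may be required on a case-by-case basis", but no rule for missing progesterone is named.
- SAP 10.7: the missing-data sensitivity analysis applies "if more than 10% of subjects have missing data on visit Day 91, 182, or 210", which concerns MPA concentrations only.
- SAP 5.2: disposition covers exclusions from analysis sets, completion, early discontinuation by reason and loss to follow-up, by treatment group.
- SAP 3.3 and 8.1: safety endpoints are summarised on the Safety Analysis Set, that is, all treated women.
- SAP Introduction: mock tables are approved "prior to un-blinding of study statisticians and maintained in a separate document", so they could not be checked.

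**The concern.** Two women who miss the same visit are handled differently because of their results. The one with a positive sample elsewhere is counted. The one whose remaining samples are all negative leaves both numerator and denominator. Each half of the rule is sensible alone: one positive settles the question, and a partial negative series does not. Together they keep the settled positives and discard the unsettled women, which pulls the percentage below the figure obtained by counting those women as delayed.

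At stake is how a safety measure reads by dose group. Delayed women have no positive sample to keep them in, so under random misses an arm with more delayed return loses more women. The exact CI describes sampling error in the women who are kept and carries nothing for this selection.

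**Working it through.** The documents state no expected delayed-return rate and no missing rate, so there is no figure of the plan's own to reproduce.

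**1. What holds without assumptions.** Among n women with at least one Week 48-52 sample, let x have five negative samples and k be dropped for a partial series with no detected ovulation.

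- Reported by SAP 8.5: x/(n−k).
- Dropped women counted as ovulated: x/n.
- Dropped women counted as delayed: (x+k)/n.

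x/n ≤ x/(n−k) because the denominator is smaller. x/(n−k) ≤ (x+k)/n reduces to k(n−x−k) ≥ 0, and n−x−k is the number with detected ovulation, so it always holds. The reported figure lies between the other two. So does the percentage that five samples would have shown in these n women, whatever caused the misses.

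**2. Worked arm of 15** (5 samples each by design; 15 per group from SAP 2.5): 6 complete negative, 2 partial negative, 7 ovulated.

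| Handling of the 2 women | Result | Exact 95% CI |
|---|---|---|
| SAP 8.5: dropped | 6/13 = 46.2% | 19.2-74.9 |
| Counted as delayed | 8/15 = 53.3% | 26.6-78.7 |
| Counted as ovulated | 6/15 = 40.0% | 16.3-67.7 |

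**3. Size against the truth, misses unrelated to ovulation.** Let D be the true delayed proportion, m the chance of missing any one visit, and j the number of the five samples at or above threshold in an ovulating woman. A delayed woman is kept with probability (1−m)^5 and an ovulating woman with probability of about 1−m^j, so the expected figure is

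D(1−m)^5 / [D(1−m)^5 + (1−D)(1−m^j)].

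With D = 0.5, m = 0.10 and j = 2: (0.9)^5 = 0.5905, giving 0.2952/(0.2952 + 0.4950) = 37.4%. With j = 1: 0.2952/(0.2952 + 0.4500) = 39.6%.

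A simulation lets j vary: progesterone above threshold for 9 days of a 21- to 35-day cycle at random phase, ovulation always found if all five samples are taken, misses independent, 600,000 women per setting. It gives:

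| True delayed | 2% missed per visit | 5% | 10% |
|---|---|---|---|
| 20% | 18.6% | 16.6% | 13.4% |
| 50% | 47.8% | 44.2% | 38.3% |
| 70% | 68.1% | 64.9% | 59.2% |

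Using 8 or 10 days instead of 9 moves the true-50% figure by at most 0.4 points. At a true 50%, an arm of 15 loses on average 0.8, 1.9 and 3.5 women to the rule, and the exact CI covers the truth 97%, 97% and 93% of the time.

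**4. Misses related to ovulation, true 50%.** If delayed women miss 5% of visits and ovulating women 20%, the rule reads 46.5%. At 2% against 20% it reads 50.4%. If delayed women miss 20% and ovulating women 5%, it reads 25.1%. The direction is not fixed.

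**5. Women with no sample at all.** Take 15 treated women of whom 6 are delayed, and let 3 of those 6 leave before Week 48, with no other misses. The truth is 6/15 = 40%. SAP 8.5 gives 3/12 = 25%, and with k = 0 both bounds among sampled women also give 3/12 = 25%. With N in the Safety Analysis Set and u without a sample, the full-set bounds are x/N and (x+k+u)/N, here 3/15 = 20% and (3+0+3)/15 = 40%, which include the truth.

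**6. What can be recovered from the planned output.** A number and a percentage give the denominator whenever the number is above zero. At zero events the exact upper limit identifies it: 21.8%, 23.2% and 24.7% for 15, 14 and 13 women. The total excluded is therefore always recoverable; its split between no-sample and partial-series women is not.

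**The case against.** The strongest reply is that a partial negative series does not settle the outcome, so leaving it out is honest, and that Version 5.0 wrote the denominator down deliberately. That stands as a reason for not counting these women as delayed in the main row. It does not remove the asymmetry, and an unsettled outcome is what bounds are for.

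A reader might go on to infer three stronger things that the documents do not support.

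- *That the rule contradicts the SAP's own definition of delayed return.* The exclusion sentence is part of that definition. Read alone, the phrase about no observed value would also count women with no samples as delayed. So (x+k)/n is a bound, not the SAP's intended estimate.
- *That women with no sample are harmless and only partial series matter.* That holds only if their dropout is unrelated to ovulation; step 5 shows the contrary case.
- *That the exclusions are hidden.* The total can be worked back. The SAP 5.2 disposition summary helps in part to separate women who left before Week 48 from those with partial series, though not exactly, and the mock tables may already show the counts.

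It is also fair that all sizes against the truth rest on assumed missing rates and steady cycling, that late visits are still to be carried out, which makes isolated misses less likely, and that coverage stays near nominal in the settings in step 3. The added rows are imperfect too. Counting partial negatives as delayed overstates a true 20% by 0.8, 1.9 and 4.1 points at 2%, 5% and 10% missing. The exact CI of the row counting them as ovulated covers a true 50% only 69% of the time at 10% missing. Both must be labelled as bounds.

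**Conclusion.** The concern holds as a minor point. Entry to the SAP 8.5 denominator depends on the outcome, and the reported figure always lies between x/n and (x+k)/n; neither statement needs an assumption. With intermittent misses unrelated to ovulation, the percentage and its exact CI are too low, by about 2, 6 and 12 points at a true 50% for 2%, 5% and 10% missed per visit. Those sizes depend on the assumed rates and cycle model.

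It would go too far to say that the percentage will be understated in this trial. If missingness depends on ovulation the direction is open, and if no visit is missed there is no effect. Nothing in the visible text offsets the rule: there is no progesterone imputation, no sensitivity analysis for this measure and no planned count of partial-series exclusions.

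The consequence is limited. The measure is secondary and descriptive, with no hypothesis test and about 15 women per arm, and the planned interim review that informs dose selection is triggered by 7.5 months of follow-up, not by Week 48-52 data.

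**What to change.** In SAP 8.5 and its table:

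1. Keep the current row, with a note that inclusion of partly sampled women depends on detected ovulation.
2. Report per arm the Safety Analysis Set N, the number with no Week 48-52 progesterone sample, and the number dropped for a partial series with no detected ovulation.
3. Among women with at least one sample, add two rows labelled as bounds and not estimates: partial-series women with no detected ovulation counted first as delayed, then as ovulated.
4. Give the same two bounds on the full Safety Analysis Set, with no-sample women also counted each way, because the pair in item 3 does not cover dropout before Week 48.

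The cost is a few sentences and a few table rows, with no new data and no change to the existing estimate. The downside is a range where there was one figure. Each dropped woman widens the sampled-women range by 1/n, or 6.7 points at n = 15, and the full-set range will be wide if many women leave early.

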8.6. Vaginal Bleeding

Subjects' responses to questions about their vaginal bleeding patterns since last visit will be summarized in frequency tables at Weeks 13, 26, and 52.

8.7. Liver Function Tests

Liver function (ALP, AST, ALT, total protein, albumin, and total and direct bilirubin) will be summarized by treatment group by tabulating mean, SD, median, minimum and maximum values at Day 7, Week 13, Week 26, and Week 52. Mean, standard error (SE), minimum and maximum change from baseline will be summarized using shift-tables, by treatment group.

8.8. Mood

A 10-item Patient Health Questionnaire will be used to produce an overall depression severity score. Depression scores will be summarized by treatment group in frequency tables (based on a 5-point Likert scale) at Day 0, Day 28, and Weeks 13, 26, and 52, and displayed graphically over time.

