^e ISRs will be evaluated on Day 0 immediately (ie, as soon as possible but no later than 10 minutes upon removing the needle) and 1 hour (\pm 5 minutes) after injection; Day 7; at Weeks 13, 26, and 52 and at other visits, if indicated. Subjects who have ISR(s) at Week 52 will be followed every 3 months (at Weeks 65 and 78) until ISR resolution or Week 78, whichever is earlier. If the subject does not have any ISRs at Week 52 it will be her final visit. All subjects will be instructed to return to the clinic if any ISRs develop after their final visit.

^f During laboratory visits, information on adverse events and concomitant medications will not be solicited, but will be documented if self-reported by the subject. Adverse events and use of concomitant medications will also be evaluated during additional ISR follow up at Weeks 65 and 78.

^g Liver function testing will be done at Screening, Day 7 and at the Weeks 13, 26, and 52.

^h Mood will be evaluated on Days 0 and 28; Weeks 8, 13, 17, 21, 26, 32, 36, 40, 44, 48, and 52.

ⁱ Vaginal bleeding pattern will be assessed at Weeks 13, 26, and 52.

^j Normal mammogram results from within the last year must be presented prior to enrollment for women 40 years of age or older.

^k Pap test will be completed for women who do not have results of their previous Pap test that are within American College of Obstetricians and Gynecologists (ACOG) Pap test standard of care requirements. If additional testing is

required based on Pap results, this should be completed prior to enrollment (in accordance with [Committee on Practice Bulletins Gynecology 2016](#)).

¹ Acceptability data will be collected at Weeks 26 and 52.

E2= Estradiol; ISR=injection site reaction; Lab = laboratory; MPA = medroxyprogesterone acetate; P= Progesterone

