5.1.5. Assessment of Mood

Subjects will be interviewed about aspects of and changes in mood at enrollment and at pre-defined timepoints throughout the study ([Table 1](#)). To measure depression or psychological distress, a selected validated scale based on the 10-item PHQ-9 ([Kroenke et al 2001](#)) will be used to ascertain the frequency of a variety of somatic and emotional indicators of well-being and produce an overall score for the severity of depression that will be compared between Day 0 and different time points in the study.

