9.6. Safety Analysis

Safety analyses will be performed on the safety analysis set. Safety measures and time points are provided in [Table 1](#).

Safety and local tolerability evaluation will be based on the following:

- occurrence of adverse events
- use of concomitant medication
- change in vital signs and body weight
- vaginal bleeding pattern
- change in mood
- change in liver function tests
- E2 levels
- delayed return to ovulation (>12 months after treatment initiation) where ovulation is defined as a single P ≥ 4.7 ng/mL
- occurrence of ISRs

No formal hypothesis tests of safety data are planned. All safety data will be summarized by treatment group using descriptive statistics (n, mean, SD, SE, median, minimum, and maximum for continuous variables, and frequency and percentage for categorical variables). Specifically, the number and percentage of subjects experiencing treatment-emergent adverse events will be

presented by treatment group, overall, by severity grade, and by relatedness to treatment. Adverse events will be further summarized in listings or frequency tables according to system organ class and preferred term. Serious adverse events and adverse events leading to withdrawal from the study will be listed separately. Concomitant medication use will be summarized by treatment group in frequency tables, by therapeutic class and medicine category. Change in vital signs (BP [systolic/diastolic], pulse, body temperature and respiration) and body weight from Day 0 to Day 7, Week 13, Week 26, and Week 52 will be described in shift tables. The percentage of women experiencing amenorrhea or vaginal bleeding disturbances (irregular vaginal bleeding or spotting) will likewise be summarized descriptively and compared between the test and reference groups. Mood data will be summarized over time from Day 0 using frequency tables and graphical displays. Liver function will be assessed by tabulating change in liver function tests from baseline to Day 7, Weeks 13, 26, and 52. Rates of return to ovulation by 12 months (Week 52), where ovulation is defined as a single $P \geq 4.7$ ng/mL, will be provided by treatment group. Estradiol concentrations will be summarized for each group using means, standard deviations, and graphical displays through Week 52. The ISR data will be provided by group in frequency tables (if applicable) and using subject-data listings.

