8.10. Estradiol

Individual E2 concentrations will be displayed graphically from pre-treatment through Week 52. E2 data will also be tabulated for each treatment group using mean, SD, median, minimum and maximum values at Day 28 and Weeks 13, 26, 30, and 52, by treatment group.

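### SAP 8.8 tabulates depression severity at 4 of 12 post-baseline assessments and plans no within-woman change or worst-value summary, short of the protocol's own comparison with Day 0

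*SAP*

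**What the plan says.** **Collection.** Protocol Table 1, footnote h, sets the schedule: "Mood will be evaluated on Days 0 and 28; Weeks 8, 13, 17, 21, 26, 32, 36, 40, 44, 48, and 52". That is Day 0 and 12 post-baseline assessments.

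**Purpose.** Protocol section 5.1.5 says the questionnaire will "produce an overall score for the severity of depression that will be compared between Day 0 and different time points in the study". Protocol section 9.6 lists "change in mood" among the criteria for the safety evaluation and adds: "Mood data will be summarized over time from Day 0 using frequency tables and graphical displays".

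**Planned analysis.** SAP section 8.8 summarizes the depression scores by arm "in frequency tables (based on a 5-point Likert scale) at Day 0, Day 28, and Weeks 13, 26, and 52", "and displayed graphically over time". It names no change score, shift table or worst-value summary. By contrast, SAP sections 8.7 (liver tests) and 8.9 (vital signs and body weight) both plan change from baseline in shift tables. The SAP introduction says the SAP prevails where it differs from the protocol, so section 8.8 decides what is reported.

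**Estradiol.** SAP section 8.10 plots individual concentrations from before treatment to Week 52 and tabulates "values at Day 28 and Weeks 13, 26, 30, and 52, by treatment group". Day 0 is not in that list.

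**The concern.** Mood is a listed safety measure, and the study is meant to support the choice of a dose that is safe and well tolerated. By-visit counts answer how many women in an arm are in each category on a given date. They do not say how many women got worse. If one woman moves from a low to a high category while another moves the other way, the counts are unchanged.

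The choice of visits adds to this. A woman who worsens at Week 8 or Week 36 and recovers before the next tabulated visit is in the low category in every table, although the study recorded her high score. With about 15 women per arm, a few such cases could change how the arms compare.

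**Working it through.** **1. Visit counts, mood.** Post-baseline assessments from Table 1, footnote h: Day 28 (Week 4) and Weeks 8, 13, 17, 21, 26, 32, 36, 40, 44, 48 and 52, which is 12. Tabulated in SAP section 8.8: Weeks 4, 13, 26 and 52, which is 4 (4/12 = 33%). Not tabulated: Weeks 8, 17, 21, 32, 36, 40, 44 and 48, which is 8. Five of these (Weeks 32, 36, 40, 44 and 48) lie between Week 26 and Week 52. The longest gap between consecutive visits is 6 weeks as collected (Week 26 to 32) and 26 weeks as tabulated (Week 26 to 52).

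**2. What short episodes would show.** The documents give no episode length, so this step is illustrative. Assume an episode of L weeks with onset s uniform over the year and no look-back by the questionnaire. A visit at week v catches it if s lies between v − L and v. The share caught is the total length of these onset intervals (overlaps counted once) divided by the length of the onset range. Two conventions are shown: onset anywhere in Weeks 0 to 52, or the whole episode inside the year (onset from 0 to 52 − L).

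| L (weeks) | Onset anywhere: 4 visits | Onset anywhere: 12 visits | Inside the year: 4 visits | Inside the year: 12 visits |
|---|---|---|---|---|
| 2 | 8/52 = 15% | 24/52 = 46% | 6/50 = 12% | 22/50 = 44% |
| 4 | 16/52 = 31% | 48/52 = 92% | 12/48 = 25% | 44/48 = 92% |
| 8 | 28/52 = 54% | 100% | 20/44 = 45% | 100% |
| 13 | 39/52 = 75% | 100% | 26/39 = 67% | 100% |
| 26 | 52/52 = 100% | 100% | 26/26 = 100% | 100% |

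Example for L = 4, onset anywhere. Visits at Weeks 4, 13, 26 and 52 each cover 4 weeks of onset, so 4 × 4 = 16 of 52. With all 12 visits the coverage is 12 × 4 = 48 of 52. The uncovered 4 weeks are 1 in each 5-week gap (Weeks 8 to 13 and 21 to 26) and 2 in the 6-week gap.

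If each interview is assumed to look back 14 days, a 4-week episode inside the year is caught with probability (4 + 6 + 6 + 2)/48 = 38% by the four visits and 100% by all 12.

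**3. Visit counts, estradiol.** Day 28, the 20 medroxyprogesterone acetate visits from Week 6 to Week 52, and the progesterone-only visits at Weeks 49, 50 and 51 give 1 + 20 + 3 = 24 post-baseline samples. With Day 0 the total is 25, which reproduces Protocol Table 4 (25 samples, 25 × 5 = 125 mL). The SAP table shows 5 of the 24 (21%) and no baseline column.

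**The case against.** **Day 0 is already in the mood table.** A reader might infer that scores are not compared with Day 0 at all. The SAP does not support that: Day 0 is one of the tabulated visits, so each arm can be read against its own baseline distribution. Protocol section 9.6 asks for frequency tables and graphs from Day 0, and SAP section 8.8 plans both. Women with a history of diagnosed depression are excluded apart from a narrow exception, so many may start in a low category, and the by-visit counts would then come closer to showing change. This narrows the gap to within-woman change and the untabulated visits; it does not remove it.

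**The other scores are not lost.** Mood is plotted over time without restriction to the tabulated visits, and the mock tables and figures are in a separate document. This stands: the right description is *not tabulated*. But SAP section 8.8 does not say whether the graph shows individuals or group summaries, and a group summary can hide one woman's episode.

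**Adverse events offer another route.** Under Protocol section 5.2.1, a safety finding that the investigator judges a clinically significant worsening is an adverse event, and SAP section 8.3 tabulates those by arm. This also stands, so such a woman need not be absent from every table in the report. The route depends on that judgement, however. All eight untabulated assessments fall at laboratory visits, where Protocol section 5.1.1 records adverse events only if the woman reports them herself.

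**Estradiol.** A reader might infer that most of the estradiol precision is discarded. The documents do not support that. Protocol section 9.6 asks only for means, standard deviations and graphs, and the precision of a by-visit mean does not depend on how many other visits are tabulated. Even for a time-averaged mean, which is not planned, the variance per woman over m visits with an assumed constant correlation ρ is proportional to (1 + (m − 1)ρ)/m. Five visits instead of 24 then lose 79% of the information at ρ = 0, 25% at ρ = 0.3 (1 − 0.329/0.44) and 13% at ρ = 0.5. The loss exceeds half only if ρ is below about 0.10.

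**Conclusion.** The point holds for mood in a limited form. SAP section 8.8 tabulates 4 of 12 post-baseline assessments as separate by-visit counts and plans no within-woman change or worst-value summary. That falls short of Protocol sections 5.1.5 and 9.6, and of what the SAP does for liver tests, vital signs and weight. The counts are exact.

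The consequence depends on assumptions. For a 4-week episode the tabulated visits catch about 25% to 31%, against 92% for all 12. By 13 weeks the figure is 67% to 75% against 100%, and at about 26 weeks there is no difference. It is therefore not established that most depression between visits would be missed; that is so only if episodes are short, roughly 8 weeks or less.

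For estradiol no protocol commitment is broken. The missing Day 0 column is a minor presentation gap. A covariate-adjusted comparison of time-averaged estradiol is not needed: it would hide the time course that the by-visit table shows, in a study with no formal safety tests.

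**What to change.** **SAP section 8.8.** Add, for each arm, a shift table of Day 0 severity category against the worst post-baseline category over all 12 assessments. Keep the by-visit table and the graph, and say whether the graph shows individual women. Report how many of the 12 assessments each woman completed, because a worst value tends to rise with the number of assessments. For the same reason, read the table as a descriptive comparison between arms, not as an absolute rate of worsening.

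**SAP section 8.10 (minor).** Add Day 0 to the estradiol table.

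**Cost.** SAP wording, one new table and one added column, all from data already collected. There are no new visits, no extra blood and no tests. Record the change in SAP section 12 with its timing relative to unblinding.
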